## **INTOMOB**

### **Administrative Information**

Project number:	1729
Trial registration number:	clinicaltrials.gov: NCT05639231 Swiss National Clinical Trials Portal: SNCTP000005259
SAP version:	1.0 (26.03.2024)
Protocol version:	7.0 (26.03.2024)

## Revision history

Revision	Justification	Timing

## 1. Introduction

### 1.1 Background and rationale

Patient confinement to bed is one of the top 5 low-value practices to avoid in hospitals according to *smarter medicine - Choosing Wisely Switzerland*, but it has been claimed to be an epidemic. While 80% of hospitalized patients could walk independently, 80% of their hospital stay is spent in bed, and only 3% ambulating or standing. Low mobility of hospitalized patients is associated with cascading problems, including persistent functional decline, institutionalization, and death. Higher hospital mobility is associated with better outcomes (e.g., fewer institutionalizations), but interventions to increase mobility have not succeeded to change clinical practice so far. Most studies did not actively involve the patients, required resources that are unavailable (e.g., more staff), or did not systematically address barriers to increase mobility (e.g., inappropriate catheters). A workable intervention must help healthcare professionals (HCPs) and patients change their behaviors and implement necessary changes in hospitals and healthcare systems.

The INTOMOB project included a pilot-study of the intervention preceding a cluster randomized controlled trial (RCT). This SAP focuses on the RCT part exclusively.

### 1.2 Objectives

The primary objective of the RCT is to evaluate the effect of a multilevel patient-empowering intervention targeting the patients, HCPs, and environment, compared to standard of care, on life-space level (i.e., the extent to which people can move from bedroom to outside town).

The second objectives are:

- 1) To evaluate the effect of the intervention, compared to standard of care, on functioning, quality of life, depression, pressure ulcer, delirium, mobility, muscle strength, fear of falling, fall-risk increasing drug (FRID) prescribing, falls, new institutionalization, discharge destination, emergency room visits, readmissions, death, and satisfaction with hospital stay.
- 2) To evaluate patient and HCP experience of the intervention (process evaluation) and characterize their perspectives on mobility after the intervention.

### 1.3 Timing of SAP writing

This SAP version was written and finalized before 50% of patients are enrolled.

## 2. Study Methods

### 2.1 Trial design

The INTOMOB RCT is a multicenter, cluster, randomized, controlled, superiority trial conducted in three hospitals in Switzerland, with a 180-day follow-up. The intervention is partially blinded. Outcome assessment and data analysis are blinded. Hospital wards are randomized in a 1:1 ratio to either intervention or control arm. Patients admitted to an intervention ward receive the intervention, while patients admitted to a control ward receive standard of care.

### 2.2 Randomization

Since the INTOMOB trial is a cluster RCT, only the wards (i.e., the clusters) have to be randomized. Ward randomization was done in a 1:1 ratio and generated shortly before start of the RCT by a statistician from CTU Bern (University of Bern, [name]). The statistician only received identifiers and not the actual names of the hospitals and wards in order to stay blind. Randomization was blocked with block size two and stratified by hospital to have the same ratio of intervention and control wards in each study center. Randomization was also stratified by ward size (<30 beds or  $\geq$ 30 beds). HCPs working on an intervention ward and participating patients admitted to an intervention ward receive the INTOMOB intervention. HCPs working on a control ward and participating patients admitted to a control ward receive the control procedure.

### 2.3 Sample size

See section 5.1 of the protocol, under “Sample size calculation for the RCT”. The calculated sample size includes a total of 274 patients (137 in each arm, and in 12 clusters in total).

### 2.4 Framework

All outcomes will be tested for superiority of the intervention arm compared to the standard of care.

### 2.5 Statistical interim analyses and stopping guidance

There is no interim analysis planned, i.e., there are no stopping rules on the individual or trial level.

### 2.6 Timing of final analysis

All outcomes will be analyzed collectively after study completion. After completion of data entry, data validation and cleaning will be performed. Data analysis will start after database lock.

### 2.7 Timing of outcome assessments

There are four time points for the patients: visit 1 at day 0, visit 2 at discharge, visit 3 at 30 (+/-5) days and visit 4 at 180 (+/-5) days. The schedule of assessments is shown in the Appendix Table 1 of the protocol. In particular, the primary outcome is assessed at visit 3.

CTU Bern	SAP for INTOMOB Based on template: CTU_STA_TEM-11; v5.0.0	Version of SAP: 0.1 Valid from: 01.12.2022	Page 7 of 20
----------	--	---	--------------

## 2.8 Blinding

The intervention is partially blinded. Complete blinding is difficult due to the nature of the intervention, the communication between colleagues working on different wards (i.e., the clusters) and the rotation of the personal (mostly the physicians) across different wards. HCPs are informed in the e-learning part of the intervention, and orally during a presentation of the study, that they should avoid speaking about the intervention with colleagues of other wards.

Outcome assessment and data analysis is blinded. The primary outcome is assessed by phone by an investigator or one of her/his designees (study nurse, doctorand, PhD student, research fellow or medical student with completed GCP training) blinded to the intervention arm. The data analyst only receives identifiers and not the actual names of the hospitals and wards in order to stay blind. Moreover, the data analyst will be blinded to the randomization group.

### **3. Data Management**

#### **3.1 Data export**

The CRFs in this trial are implemented electronically using a dedicated electronic data capturing (EDC) system (REDCap, <https://www.project-redcap.org/>). The EDC system is activated for the trial only after successfully passing a formal test procedure. All data entered in the CRFs are stored on a Linux server in a dedicated Oracle database. Responsibility for hosting the EDC system and the database lies with CTU Bern.

At final analyses, data files will be extracted from the database via the database interface into statistical packages to be analyzed. After database lock, the status of the database is recorded in special archive tables.

#### **3.2 Data validation**

First line data validation is performed by the online eCRF system at real-time as defined in the data dictionary. Second line data validation and cleaning will be performed after completion of data entry but before database lock according to the SOP for data validation.

#### **3.3 Data preparation**

Data preparation will be performed according to the SOP for data preparation.

#### **3.4 Data sharing**

If required and budgeted by the sponsor, data sharing will be performed according to the SOP for data sharing.

## 4. Statistical Principles

### 4.1 Confidence intervals and *P* values

All effect measures will be accompanied by a two-sided 95% confidence interval. All applicable statistical tests will be two-sided and will be performed using a 5% significance level.

### 4.2 Analysis populations

#### 4.2.1 Full analysis set (FAS)

The full analysis set (FAS) will include all randomized wards and all enrolled subjects. Following the intent-to-treat principle, wards and subjects will be analyzed according to the assigned intervention.

#### 4.2.2 Per-protocol (PP)

The per-protocol population consists of all wards and subjects in the FAS that do not have any protocol deviations that could confound the interpretation of analyses conducted on the FAS. An eCRF dedicated to protocol deviations is implemented in the database. This will allow to determine the patients for whom such deviation occurred. Protocol deviations will be defined as at least one of the following:

- Discharge earlier than 3 days after enrolment
- Change from an intervention to a control ward or from a control to an intervention ward
- Any of the eligibility criteria not fulfilled

#### 4.2.3 Safety population

Not applicable.

### 4.3 Estimands

#### 4.3.1 Primary outcome on the FAS

**Outcome of interest:** life-space assessment at 30 (+/-5) days

**Patient-set of interest:** full analysis set

**Handling of intercurrent events:** if the primary outcome is missing in more than 5% of patients, we will employ multiple imputation in the primary analysis and additionally perform an available case analysis as sensitivity analysis disregarding missing data.

**Population-level summary measure of outcome:** absolute difference with 95% confidence interval, computed using generalized estimated equations (GEEs) with Gaussian distribution, exchangeable correlation structure and robust standard errors with small sample correction.

## 5. Trial Population

### 5.1 Screening data

The number of screened patients will be reported if available.

### 5.2 Eligibility

The inclusion criteria are:

- Admission to a general internal medicine (GIM) ward of a participating hospital,
- Age  $\geq$  60 years,
- Being ambulatory during the 2 weeks before admission (self-report),
- Living in the community (not in a nursing home or another institution) for at least the last 30 days prior to admission,
- Ability to understand French or German,
- Planned length of stay at least 3 days after enrollment.

The exclusion criteria are:

- Medical contraindication to walk (e.g., wound not allowing loading weight),
- Wheelchair-bound,
- End-of-life,
- Severe psychiatric disorder (severe depression, schizophrenia, psychosis),
- Delirium (according to the Confusion Assessment Method [CAM]),
- Cognitive impairment making impossible to use study material (i.e., to implement the intervention) and to understand and sign informed consent, based on clinical judgement, except if a proxy can be actively involved in the study and provides consent,
- Severe visual impairment.

### 5.3 Recruitment

A CONSORT patient flow diagram will be drawn following the CONSORT 2010 standards (<http://www.consort-statement.org/consort-2010>).

### 5.4 Baseline patient characteristics

Table 1 shows the list of baseline characteristics to be summarized. Continuous and count variables are presented as mean with standard deviation or median with quartiles, as appropriate. Categorical variables are presented as absolute and relative frequencies. Those variables will be presented by randomization group (intervention vs. control).

Table 1: Baseline table.

Description	Variable	Type
Age	age	Continuous [years]
Sex	sex	Categorical: female, male

Description	Variable	Type
Body mass index	weight_kg/height_cm	Continuous [kg/m  ]
Hospital	Hospital	Categorical: Inselspital, HFR, KSB
Number of hospitalizations in the last 180 days before admission	hosp_previous_n	Count
Support: home care	homecare	Binary: yes, no
Support: household help	household	Binary: yes, no
Support: mobility aid at admission	mobility_aid	Binary: yes, no
Life-space assessment		
Barthel Index (ADLs)	barthel_total	Continuous [range 0-100]
EQ-5D VAS	eq5d5l_vas2_uk_eng	Continuous [range 0-100]
DEMMI	demmi_score	Continuous [range 8-100]
Main diagnosis	hosp_cause	List of diagnosis categories
Number of medications at admission	med_n	Continuous

## 5.5 Adherence and protocol deviations

The occurrence of protocol deviations and non-compliance to the intervention (as defined in section 4.2.2) will be checked and reported in a table as well as in the flow chart (see paragraph 5.3).

## 5.6 Withdrawal/follow-up

Number and percentage of withdrawal and lost to follow-up will be presented in the flow chart.

## 6. Analysis

### 6.1 Outcome definitions

Table 2: Derivation of primary and secondary outcomes.

Outcome	eCRF sheet	Variable	Variable type	Derivation	Outcome type
Primary outcome: Life-space level or Life-space level for institutional setting at D30 [range 0-120]	Life-Space As- essment or Life-Space As- essment for in- stitutional setting (note: LSA and LSA-IS can be merged; same coding except with " is" in ad- dition [e.g., "ls1_yn_fu_is_d 30"])	ls1_yn_fu_d30	Binary: No, Yes	ls1_yn_fu_d30 * ls1_frequency_fu_d30 * [(2 if equipment=No and personhelp=No) OR (1.5 if equipment=Yes and personhelp=No) OR (1 if personhelp=Yes)] + 2 * ls2_yn_fu_d30 * ls2_frequency_fu_d30 * [(2 if equipment=No and personhelp=No) OR (1.5 if equipment=Yes and personhelp=No) OR (1 if personhelp=Yes)] + ... + 5 * ls5_yn_fu_d30 * ls5_frequency_fu_d30 * [(2 if equipment=No and personhelp=No) OR (1.5 if equipment=Yes and personhelp=No) OR (1 if personhelp=Yes)]***	Continuous
	ls1_frequency_fu_d30		Categorical: 1: <1x/week, 2: 1-3x/week, 3: 4-6x/week, 4: daily		
	ls1_equipment_fu_d30		Binary: No, Yes		
	ls1_personhelp_fu_d30		Binary: No, Yes		
	(Same variables with numbers from 2 to 5)				
Secondary outcomes					
1) Life-space level at D180				Same as primary outcome, with _d180 instead of _d30	
2) Activities of daily living (ADLs) at D30 and D180	ADLs (Barthel Index)	barthel_total_d30 / barthel_total_d180		Continuous [range 0-100]	Continuous
3) Instrumental activities of daily living (IADLs) at D30 and D180	IADLs (Lawton scale)	iadl_total_d30 / iadl_total_d180		Continuous [range 0-8]	Continuous

4) Quality of life at D30 and D180 (EQ-5D-5L VAS)	EQ-5D-5L	eq5d5l_vas2_uk_eng	Continuous [range 0-100]	Continuous
5) Depression at D30 and D180	Depression (PHQ-2)	depression_phq_2_d30/_d180	Binary (Yes/No)	Binary (yes/no)
6) Pressure ulcer at hospital discharge	Pressure ulcer	ulcer_yn_discharge	Binary (Yes/No)	Binary (yes/no)
7) Delirium during hospitalization	Delirium (Confusion Assessment method)	delirium_discharge	Binary (Yes/No)	Binary (yes/no)
8) Mobility at hospital discharge (DEMMI score)	Mobility: DEMMI	demmi_score_discharge	Continuous [range 0-100]	Continuous
9) Lower-limb muscle strength at hospital discharge	Muscle strength	strength_knee_discharge	Continuous 0-5 (from no activity to complete range of motion)	Continuous
10) Hand-grip muscle strength at hospital discharge	Muscle strength	strength_dynamo1_discharge, strength_dynamo2_discharge, strength_dynamo3_discharge	Continuous	Best of three attempts
11) Level of activity during hospitalization (% in light, moderate, [very] vigorous)	Accelerometer output	accelero_activity_level [% in light activity], acelero_activity_level_2 [% in moderate activity], acelero_activity_level_3 [% in (very) vigorous activity]	Continuous	Continuous
12) Level of activity during hospitalization (intensity of movement: vector magnitude CPM)	Accelerometer output	Accel_vm_cpm	Continuous	Continuous
13) Fear of / concerns about falling at discharge, D30 and D180	Falls Efficacy Scale – International	fes_i_total_d30/d_180	Continuous [range 16-64]	Continuous
14) FRID prescribing at hospital discharge	Medication classes at discharge	med_frid_discharge	Binary (Yes/No)	Binary (yes/no)
15) FRID prescribing at hospital discharge, D30 and D180	Medication classes at D30-D180	med_frid_discharge_fu_d30, med_frid_discharge_fu_d180	Binary (Yes/No)	Binary (yes/no) and

16) Falls during hospitalization and within D30 and D180	Falls	falls_yn_discharge1 / falls_yn_d301 / falls_yn_d180 (1 => repeated instrument);	Binary (yes/no)	Sum the number of falls for the count analysis	Binary (yes/no) or count
17) New institutionalization at hospital discharge and within D30 and D180	New institutionalization	new_institutionaliza_v_11_d30/d180 instit_date_d30/d_180	Binary (Yes/No) Date		Time- to event
18) Discharge destination	Index hospitalization – discharge data	Discharge_destination	Categorical [home, family (not own home), rehabilitation, nursing home permanent, nursing home temporary, other hospital, other institution, acute geriatrics, palliative ward, same hospital other ward, ICU, death, other]		Categorical
19) Emergency room visits within D30 and D180	Emergency room visits	er_visit_yn_30d1 (1 => repeated instrument); for between D30 and D180: same variable with “_180” instead of “_30” Date: er_visit_date_30d1 / _180d1	Binary (yes/no) Date	Sum the number of readmissions for the count analysis	Time-to-event or count
20) Readmissions within D30 and D180	Readmissions	readmission_yn_30_d1 (1 => repeated instrument); for between D30 and D180: same variable with “_180” instead of “_30” Date: readmission_30d1 / _180d1	Binary (yes/no) Date	Sum the number of readmissions for the count analysis	Time-to-event or count
21) Death within D30 and D180	SAE	death_date	Date		Time-to-event

22) Satisfaction with hospitalization evaluated at hospital discharge	Satisfaction with hospitalization	satis_nursing_1-5 satis_med_1-5 satis_physio_1-5 satis_info_1-3 satis_autonomy_1-2 satis_support_1-3	Ordinal (for each: dissatisfied, rather dissatisfied, neutral, rather satisfied, satisfied, not applicable)	Summary of all variables, and separately for each of the 6 domains	Continuous,
---	-----------------------------------	---	---	--	-------------

\*\*\* See the paper <https://doi.org/10.1093/ptj/85.10.1008> for detailed explanation on this score calculation. LSA will range from 0 (totally bed bound) to 120 (traveled out of town every day without assistance).

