## 6.2 Analysis methods

### 6.2.1 Primary analysis

The primary analysis will be an intention-to-treat analysis to compare the life-space assessment (LSA) between intervention and control groups at D30. LSA will be analyzed using GEEs with Gaussian distribution, exchangeable correlation structure and robust standard errors with small sample correction. This model accounts for the cluster design as well as for the small number of clusters and will be adjusted for the baseline LSA. The absolute difference between intervention group and control group will be presented with a 95% confidence interval (CI).

Continuous secondary outcomes will be evaluated likewise, adjusting for the baseline value if applicable. If outcome measures are non-normally distributed, we will apply an adequate distribution in GEE (e.g., gamma) or log-transform the outcome measure before analysis. Absolute differences between intervention group and control group will be presented with a 95% CI.

Binary outcomes will be analyzed using a GEE with a binomial distribution, a logit link, an exchangeable correlation structure and robust standard errors. Relative differences between groups will be presented as odds ratio with 95% CI.

Count outcomes will be analyzed using a GEE with a negative binomial distribution, a log link, an exchangeable correlation structure and robust standard errors. Relative differences between groups will be presented as rate ratio with 95% CI.

Time-to-event outcomes will be analyzed using a Cox regression model. To account for clustering, we will use shared frailties for clusters as well as cluster robust standard errors. Relative differences between groups will be presented as hazard ratio with 95% CI.

Categorical outcomes (discharge destination) will be analyzed using multinomial logistic regression with robust standard errors to account for clustering. Relative differences between groups will be presented as rate ratios with 95% CI.

Readmissions and emergency room visits will be analyzed as time-to-event outcomes, except if we notice that those outcomes often happen multiple times. In such case, we will analyze them as count outcomes.

Mortality and time to new institutionalization will be analyzed as time-to-event.

Falls will be analyzed as binary outcomes. If we notice that this outcome often happens multiple times, we will analyze it as a count outcome.

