## **6.8 Quality control**

A data analyst from CTU will perform a double programming of the primary analysis as well as a quality control of the final statistical report.

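### Table 2 of the SAP derives the emergency-room-visit count from readmissions, contradicting the row's own variables (a minor one-cell correction)

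*SAP*

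**What the plan says.** Table 2 in SAP section 6.1 sets out, outcome by outcome, the eCRF sheet, the variables, the derivation and the outcome type.

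Item 19 is "Emergency room visits within D30 and D180". Its source variable is given as "er_visit_yn_30d1 (1 => repeated instrument"), with a matching date field. Its derivation cell reads "Sum the number of readmissions for the count analysis".

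Item 20, readmissions, has its own sheet and its own variable, "readmission_yn_30_d1 (1 => repeated instrument"), and the same derivation sentence.

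Section 6.2.1 says when a count is used at all: "Readmissions and emergency room visits will be analyzed as time-to-event outcomes, except if we notice that those outcomes often happen multiple times". If they do recur often, both are treated as count outcomes, with a negative binomial GEE, log link and rate ratio.

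**The concern.** Table 2 is the specification from which the outcome variables are to be built, so its derivation column is an instruction to the programmer. In item 19 that instruction names a different event from the one the row defines.

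If the count analysis is used and the cell is taken at its word, the emergency-room visits recorded on their own instrument would not be counted at all. A readmission result would be reported under the emergency-room label. The same derived variable would then pass into the per-protocol analysis (section 6.2.2) and the sensitivity models (section 6.2.3).

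**Working it through.** The plan gives no figure to reproduce here. The check is to compare the three rows of Table 2 that carry a count derivation, and then to read section 6.2.1.

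| Table 2 item | eCRF sheet | Source variable | Event named in the derivation | Agrees with its own row? |
|---|---|---|---|---|
| 16, falls | Falls | `falls_yn_...` | falls | yes |
| 19, emergency room visits | Emergency room visits | `er_visit_yn_30d1` and the `_180` equivalent | readmissions | **no** |
| 20, readmissions | Readmissions | `readmission_yn_30_d1` and the `_180` equivalent | readmissions | yes |

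1. **Intended pattern.** Item 16 says "Sum the number of falls for the count analysis". Each row is meant to add up its own events. Items 16 and 20 do so; item 19 does not.

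2. **Extraction error?** Unlikely. Items 19 and 20 each run complete from outcome name to outcome type, and each contains the derivation sentence once. Nothing appears to be shifted or blacked out. It looks like text carried over from item 20.

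3. **Is it corrected elsewhere?** No. Section 1.2 lists emergency room visits and readmissions as separate objectives, and section 6.2.1 names both, but neither section gives another derivation for the emergency-room count. Section 7 lists no deviation that would explain building one from the other.

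4. **Literal consequence.** For patient *i* over a given follow-up window, let E*i* be the number of emergency-room entries and R*i* the number of readmission entries.
   - Item 19 as its variables imply: Y19*i* = E*i*.
   - Item 19 as its derivation cell reads: Y19*i* = R*i*.
   - Item 20: Y20*i* = R*i*.

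   Under the literal reading Y19*i* = Y20*i* for every patient. The same count model fitted to the same numbers returns the same rate ratio and interval.

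5. **When this applies.** Only when the count analysis replaces the default. The time-to-event analysis of item 19 draws on the emergency-room date field and does not use the faulty cell.

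**The case against.** The strongest reply is that this is a slip that few programmers would act on. The outcome name, the sheet, the variable and the date in item 19 all point to emergency room visits. The row lists no readmission variable, so the rule cannot be run on its own inputs; the wrong count requires someone to borrow fields from item 20. The count analysis is also a fallback for a secondary outcome. All of this stands and sets the severity. It does not make the cell right: a programmer who does the sensible thing departs from the written specification without a record of it.

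Three stronger readings are tempting, and the SAP does not support them.

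- **That the emergency-room result will be wrong.** It would be wrong only if the count switch is made and the one cell is followed against the rest of its row.
- **That quality control could not catch it.** Section 6.8 provides for "double programming of the primary analysis", which might suggest that secondary outcomes go unchecked. The same sentence also provides for a check of the final report, where two identical rate ratios could be noticed. The scope of the double programming is itself unclear, because the section headed as the primary analysis (6.2.1) also contains the models for the secondary outcomes.
- **That the SAP must say whether an emergency visit ending in admission counts under item 19, item 20 or both.** The slip does not raise that question. The two events have separate sheets and variables, and event definitions of this kind may sit in the protocol.

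**Conclusion.** The derivation cell of item 19 is wrong as written: it contradicts the row's outcome, sheet and variables, and it duplicates item 20. Severity is minor.

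If it takes effect, the error is complete for the affected analysis, because the emergency-room count would be the readmission count. That rests on two conditions: the count analysis in section 6.2.1 is triggered for emergency room visits, and the cell is followed literally. Reporting the same rate ratio twice also requires readmissions to be analysed as counts. If only the emergency-room outcome were switched, its label would still be attached to a readmission rate ratio, but without an identical twin in the report.

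The default time-to-event analysis, the primary life-space outcome and the sample size are untouched.

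**What to change.** Replace the derivation in Table 2, item 19 with: *Count analysis: sum the emergency room visits (`er_visit` repeated-instrument entries)*. Leave item 20 as it stands.

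Enter the change in the SAP's revision history before database lock, so that the rule is correct before anyone sees whether the count analysis is needed. The cost is one table cell, with no new data and no change to any model.
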